7.6 Expected SAEs/ SARs and non-reportable events

Expected SAEs / SARs and non-reportable events will be recorded in children's case report forms.

7.7. Pregnancy

Not applicable (preschool children only).

7.8 Overview of the Safety Reporting Process

An overview of the safety reporting process is presented in section 7.3 of this protocol.

7.9 Pharmacovigilance responsibilities

Pharmacovigilance responsibilities will be shared by the Sponsor and by the Chief Investigator and co-investigators.

8 Data Handling and Record Keeping

8.1 Confidentiality

Children's personal data will remain confidential, and will be handled, processed, stored and destroyed according to the terms of the Data Protection Act 1998.

8.2 Study Documents

Study documentation will be maintained in a Trial Master File, to be stored at the Centre for Paediatrics, Barts and The London Medical School.

8.3 Case Report Forms

Case Report Forms will include the following data: children's demographic details, medical history, concomitant medications, checklist of eligibility criteria, and records of administration of IMP.

8.4 Record Retention and Archiving

Trial records will be retained for 20 years. Records will be stored in the Centre for Paediatrics, Barts and The London Medical School while the study is being conducted, after which they will be transferred to the Barts and the London Trust archive.

8.5 Compliance

The CI & PI will ensure that this study is conducted in accordance with the latest version of the "Declaration of Helsinki" (http://www.wma.net/e/policy/b3.htm), the UK Legal Framework for Clinical Trials of Investigational Medical Products (SI 2004/1031) and subsequent relevant

WAIT Trial_ Protocol_v7_24th June 2011

Page 36 of 58

amendments. The study will adhere to the principles outlined in the Guidelines for Good Clinical Practice.

8.6 Definition of the end of the study

The end of the study will be defined as the date of the final study visit of the final participant undergoing follow-up.

9 Clinical governance issues

9.1 Ethical considerations

The main ethical considerations arising from the design and conduct of this trial are as follows:

9.1.1 Rationale for research

Ethical research must be informed by existing research, and investigate an important question. We have addressed this issue by thorough review of the existing literature, and our own data showing increased leukotriene activation in preschool wheeze⁵. There is a consensus among investigators that clinical trials of parent-initiated montelukast are needed to determine whether montelukast can reduce the risk of a severe exacerbation of wheeze leading to need unscheduled medical attention.

9.1.2 Design of research

Ethical research must employ the most appropriate design in order to answer the research question. When investigating efficacy of a clinical intervention, a double blind, randomised, placebo-controlled trial is the gold standard methodology.

9.1.3 Minimisation of inconvenience, discomfort and risk for participants

Ethical research must seek to minimise potential inconvenience, discomfort and risk that children and their parents may experience during the course of a study. The principle inconveniences of the study arise from the time spent by parents to attend for the screening visit and Visit 2 where the IMP will be issued. We have sought to minimize these by providing reimbursement of reasonable travel expenses incurred as a result of participation in the study. The principle discomfort involved arises from collecting samples for DNA analysis. We have sought to minimize this by using a specially designed saliva collection system for infants (Oragene-infant DNA collection system) which does not need scraping of the buccal mucosa. The risks associated with montelukast therapy are very low, with no significant risks reported. We have sought to minimise this further by review by the data monitoring committee of accumulating data relating to adverse events.

9.1.4 Recruitment procedure

Ethical research projects should seek to recruit children from all ethnic backgrounds, and not be restricted to those fluent in the English language. To reduce misunderstandings and to maximise recruitment and adherence of ethnic minorities, the research nurse in London will

WAIT Trial_ Protocol_v7_24th June 2011

Page 37 of 58

use a Sylheti interpreter when appropriate and translations of the information sheet will be available in Bengali and Gujarati (the main minority languages in Leicester and East London) at all sites where they are required.

9.1.5 Confidentiality

Ethical research projects should ensure that participants' personal data remain confidential. Our procedures for handling, processing, storage and destruction of data are compliant with the Data Protection Act 1998.

9.1.6 Data Handling and Record Keeping

Case report forms will be anonymised and held in locked filing cabinets in the local recruitment centres and in the Centre for Paediatrics, Paediatric Pragmatic Clinical Trial Section, Barts and The London School of Medicine and Dentistry. Only trial staff will have access to these.

Trial staff will enter all non-patient identifiable data from case report forms into an electronic database held on a password protected computer, linked to an ID code which will be unique for each trial participant. One electronic copy of this database will subsequently be stored on a password-protected file on the Chief Investigator's password-protected G-drive on the QMUL network; a back-up copy will be held on a password-protected file on the C drive of a stand-alone desk-top computer kept in a locked office in the Centre for Health Sciences, Barts and The London School of Medicine and Dentistry. Trial staff and representatives of the sponsor, participating NHS Trusts or regulatory authorities will be the only people with potential access to view study data that could be linked to patient identifiable data.

9.2 Summary monitoring plan

The CI will ensure that the Barts and the London monitoring template is completed in a continuous fashion throughout the study and kept up to date by the CI/co-investigators (for the first part of the report) and by the monitor to be appointed (for both the first part and the source data verification part of the template). This trial uses IMPs licensed in the UK and used within their marketing authorisation. The monitoring report will be sent to the JRO six months after the first consent form has been signed and bi-annually thereafter. The sponsor will carry out random on-site monitoring checks to ensure that the reports have been completed accurately.

9.3 Audit and inspection

Trial documentation will be made available to auditors and inspectors representing the Sponsor and the regulatory authorities.

9.4 Reporting of Serious breaches in GCP or trial protocol

Serious breaches in GCP and serious breaches of the trial protocol will be reported to the sponsor.

WAIT Trial_ Protocol_v7_24th June 2011

Page 38 of 58

9.5 Quality Assurance

Data quality will be audited according to GCP guidelines, and a trail will be maintained of any change or correction to the case report form or the electronic database. The sponsor will have direct access to all trial-related sites, source data and reports in order to ensure that the trial is conducted, and data are generated, recorded and reported in compliance with the protocol and with Good Clinical Practice.

9.6 Data Monitoring Committee

A data monitoring committee (DMC) has been established for the trial. The chairman of the DMC will keep a record of DMC communications and activities. The central responsibility of this DMC will be to make recommendations to the Sponsor and the Chief Investigator on further conduct of this trial, based on results of the monitoring procedures described below. Such recommendations could include continuing or terminating the trial, or modifying its protocol. Any such modifications should not violate the concepts behind the original study protocol. If changes in the study conduct are recommended by this DMC, sufficient information should be provided to allow the sponsor and chief investigator to decide whether and how to implement them. The implementation of any DMC recommendation is the responsibility of the sponsor and chief investigator who are also free to neglect (in whole or in part) any recommendations of this DMC. The sponsor and the investigators bear the final responsibility for the conduct of the trial. This responsibility cannot be transferred to the DMC.

9.6.1 Maintenance of trial treatment randomisation codes and procedures for breaking codes.

The trial treatment randomisation code will be generated by Nova Laboratories Ltd as described above. Nova Laboratories Ltd will email a copy of this code to the Trials pharmacist at the participating sites hospital pharmacy. A member of the participating sites hospital pharmacy staff may unblind a participant's allocation at the request of a Principal Investigator, according to the WAIT Trial Standard Operating Procedure for emergency code breaking.

9.6.2 Monitoring procedures

The DMC will review accumulating data in a blinded fashion in order to monitor safety, efficacy and quality of study conduct. The DMC may also request data presented in an unblinded form.

a) Safety monitoring

The DMC may ask for an analysis to compare the incidence of fatal/life-threatening events and other SAE between the 2 groups, and report any need for changes in the conduct of the trial to the Steering Committee.

b) Efficacy monitoring

No interim efficacy analysis will is planned.

WAIT Trial_ Protocol_v7_24th June 2011

Page 39 of 58

c) Monitoring quality of study conduct

If the DMC observes problems with the study conduct (e.g. with respect to protocol adherence or withdrawal of children), it should consider making recommendations to the investigators and the sponsor to improve the quality of the study.

9.6.3 Declaration of possible conflicts of interest of DMC members

The members of this DMC have no involvements that might raise the question of bias in their reports to the Trial Steering Committee in this study. Specifically, they have no financial interest in the outcome of this study, and they will not be authors on publications arising from this study.

9.6.4 Frequency and format of DMC meetings

It is anticipated that the DMC will be able to conduct all of its business by email and telephone call, rendering a physical meeting between members, investigators and representatives of the sponsor unnecessary. It is planned that the DMC will assess safety data every six months. The DMC will decide whether the frequency of monitoring needs to be changed at any point during the trial.

9.6.5 Communication Procedures

The DMC will report directly to the Trial Steering Committee.

9.6.6 Responsibilities, timelines and methodological aspects

The DMC will operate according to a charter, agreed to by all members. There will be no planned interim efficacy analysis.

9.6.7 Documentation of the DMC activities

The chair of the DMC will be responsible for ensuring the safe storage of DMC confidential reports and meeting minutes.

9.6.8 Parental Advisory Group (PAG)

Each original Centre will convene a parental advisory group consisting of at least 4 families with a child who has or had preschool wheeze and who was not recruited in the trial. Parents will guide researchers on how to approach families, will comment on the results of the qualitative interviews, and advise on how best to disseminate the trial's results. The PAG will be chaired by the local PI and will be co-ordinated by [name]. Centres that are subsequently added will not be required to convene a parental advisory group.

10 Statistics

10.1 Endpoints

10.1.1 Primary endpoints

The primary outcome measure for this trial is:

 Number of times a child attends for an unscheduled medical opinion with respiratory problems over a 12 month period as confirmed from clinical records.

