Study Centres	Barts and The London NHS Trust; University of Leicester NHS Trust, Grampian NHS Trust (others may be added as required – see appendix)					
Primary objective (phase of trial)	To determine whether parent-initiated intermittent treatment with oral montelukast in preschool children reduces the need for unscheduled medical attention for upper or lower respiratory tract infection or wheeze (Phase 3 trial).					
Number of Subjects/Patients	1300					
Main Inclusion Criteria	 Medical record diagnosis of wheeze, two previous attacks of wheeze one being within the last 3 months. Age ≥ 10 months and ≤ 5.0 years at recruitment 					
Statistical Methodology and Analysis	The incident rate ratio (relative risk) and 95% confidence interval for need to seek unscheduled medical attention.					

Glossary of Terms and Abbreviations

AE Adverse Event

ACT Asthma Control Test
AR Adverse Reaction

ALOX5 membrane bound 5-lipoxygenase

ASR Annual Safety Report
CA Competent Authority

Child An individual who takes part in this clinical trial

CI Chief Investigator

CRF Case Report Form

CRO Contract Research Organisation

CTA Clinical Trial Authorisation

CTIMP Clinical Trial of Investigational Medicinal Product

DMC Data Monitoring Committee

EC European Commission

EMEA European Medicines Agency

EU European Union

EUCTD European Clinical Trials Directive
EudraCT European Clinical Trials Database

EudraVIGILANCE European database for Pharmacovigilance

GAFREC Governance Arrangements for NHS Research Ethics

GCP Good Clinical Practice

GMP Good Manufacturing Practice

IB Investigator Brochure
ICF Informed Consent Form

IMP Investigational Medicinal Product

IMPD Investigational Medicinal Product Dossier

ISRCTN International Standard Randomised

IVDMIA In vitro diagnostic multivariate index assay

JRO Joint Research and Development Office

MA Marketing Authorisation

MHRA Medicines and Healthcare products Regulatory Agency

WAIT Trial_ Protocol_v7_24th June 2011 Page 15 of 58

Protocol as approved by National Research Ethics Service Reference 09/H1102/110 Date 23rd November 2009 MS Member State

Main REC Main Research Ethics Committee

NHS R&D National Health Service Research & Development

PAG Parental Advisory Group

PI Principle Investigator

QA Quality Assurance

QC Quality Control

QP Qualified Person for release of trial drug

RCT Randomised Control Trial

REC Research Ethics Committee

SAR Serious Adverse Reaction

SAE Serious Adverse Event

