1.5.2 Benefits

A recent audit of "asthma" admission in children covering 67 hospitals during the period 1998-2005, found that 75% of 9,429 admissions were for preschool wheeze³. Since this was a secondary care-based audit, it very likely underestimates the total number of unscheduled attendances for preschool wheeze. A therapy that reduces the number of severe attacks will therefore have a major benefit to the NHS and children.

2 Study Aims and Objectives

The principal objective of this research is to determine whether intermittent treatment with oral montelukast in preschool children reduces the need for unscheduled medical attention for wheeze. Treatment (IMP) will be initiated by parents or guardians at the onset of every viral upper respiratory tract infection or wheezing episode and continued for 10 days.

3 Investigational plan

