10.1.3 Study definitions

- **1. Need for unscheduled medical attention** will be defined as an episode requiring an unscheduled attendance to either a general practitioner, or to an accident and emergency department, or a combination of both where wheeze is diagnosed by a clinician.
- **2. Time from randomisation to first attack of severe wheeze** will be defined as the number of days from the date of administration of first dose of IMP to the first date on which a wheeze exacerbation attains criteria of severity stated in 1 above.
- **3. Number of days with parent-reported wheeze** will be defined as the number of days with wheeze over the 12 month trial period obtained by telephone contact with the researcher and diary card.
- **4.** Use of inhaled relief medication, expressed as total number of occasions used over **12 month period**, and mean number per wheeze episode will be obtained from the number of actuations calculated by diary card reporting.

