10.2 Statistical considerations

10.2.1 Sample Size

This trial is powered to detect a clinically significant difference in the number of attacks of wheeze between intervention and control arms. We also have some power to detect differential responsiveness (in terms of the primary outcome) to montelukast in the stratum with ALOX5 promoter polymorphism [5/5], compared with the stratum with the ALOX5 [5/x and x/x]" genotype.

Baseline data on mean (0.76) and standard deviation (1.22) of number of attacks are based on data from the UK General Practitioner Research Database on courses of oral steroids (a proxy for number of episodes). These data follow an overdispersed Poisson distribution. To take account of this we used markov chain Monte Carlo simulation in WinBUGs to estimate sample sizes required: (WinBUGS Version 1.4. 2003 Available from: http://www.mrc-bsu.cam.ac.uk/bugs/welcome.shtml). To detect a 33% drop in attack rate requiring medical attention, with a power of 90% and at a significance level of 5%, and a 6% loss to follow up, we require 1050 children in total. A 33% drop in attack rates equates to an attack rate of 0.51 for the treatment group. The clinical significance of these changes is that approximately four children will need to be treated to prevent one clinically severe attack. A sample size of 1200 gives just over 80% power at the 5% significance level to detect an interaction between treatment and genotype if the effect is a 60% reduction in the [5/x plus x/x] and a 20% reduction in the [5/5] stratum. Assuming a 6% dropout, 1300 children will need to be recruited.

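### The primary endpoint is stated inconsistently (any respiratory attendance or clinician-diagnosed wheeze episode), and the stated power belongs to a wheeze count rather than to the endpoint in 10.1.1

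*Protocol*

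**What the plan says.** Five places in the protocol bear on the primary event.

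- **10.1.1 Primary endpoints:** "Number of times a child attends for an unscheduled medical opinion with respiratory problems over a 12 month period as confirmed from clinical records".
- **Study Summary, primary objective:** whether treatment "reduces the need for unscheduled medical attention for upper or lower respiratory tract infection or wheeze". The statistical row of the same table gives the analysis as "The incident rate ratio (relative risk) and 95% confidence interval for need to seek unscheduled medical attention".
- **Section 2, principal objective:** whether treatment "reduces the need for unscheduled medical attention for wheeze".
- **10.1.3, definition 1:** need for unscheduled medical attention is an episode with an unscheduled visit to a GP, to A&E, "or a combination of both where wheeze is diagnosed by a clinician".
- **10.2.1 Sample Size:** the trial is "powered to detect a clinically significant difference in the number of attacks of wheeze between intervention and control arms". The inputs are "Baseline data on mean (0.76) and standard deviation (1.22) of number of attacks", taken from oral-steroid courses as a proxy for episodes.

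No section says which of these governs.

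**The concern.** The conflict has two parts.

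**Cause.** 10.1.1 and the Summary objective admit any respiratory problem or infection. Section 2, 10.1.3 and 10.2.1 are confined to wheeze, and 10.1.3 also requires a clinician to have diagnosed it. Parents start the trial medication at a cold as well as at wheeze (Section 2, 5.4), so visits for infection without wheeze are to be expected. The efficacy evidence in 1.1 and 1.4.2 is about wheeze, asthma symptoms and exacerbations, and 1.5.1 reports a slight excess of upper respiratory infection on montelukast. The two counts may therefore show different treatment effects.

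**Unit.** A GP visit followed by A&E in the same illness is two events under 10.1.1 and one under 10.1.3.

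At stake are what the primary rate ratio estimates, whether the stated power applies to it, and whether the primary event could be settled after data are seen. This is not detail to be left to an analysis plan, because an analysis plan cannot be checked against a protocol that gives two answers.

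**Working it through.** **1. The plan's own figure.** Inputs from 10.2.1: control mean 0.76, SD 1.22, treated mean 0.51 (difference 0.25), power 90%, alpha 5% (two-sided assumed), loss 6%.

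Two-means formula: n per arm = 2 × 1.22² × (1.960 + 1.282)² / 0.25² = 501. The total is 1002, and 1002 / 0.94 = 1066 (1060 with the difference at 0.2508). At N = 1050, with 493.5 evaluable per arm, power is 89.6%. So 1050 at 90% roughly reproduces, for a wheeze-attack count. The protocol used simulation, which cannot be rerun from the text.

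**2. Model for the illustration.** Negative binomial with k = (1.22² − 0.76) / 0.76² = 1.26. For control and treated means μ0 and μ1 with n per arm:

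power = Φ( |ln(μ1/μ0)| / √[(1/μ0 + 1/μ1 + 2k)/n] − 1.96 )

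This is more optimistic than the protocol: it gives about 96% at N = 1050, where 10.2.1 states 90%. Its results should be compared with each other, not with the 90%. With 1300 × 0.94 = 1222 evaluable (611 per arm) and rate ratio 0.67, the wheeze-only count gives 0.4005 / 0.0974 − 1.96 = 2.15, so 98%.

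**3. Adding non-wheeze attendances.** Let a share f of control attendances be non-wheeze. The documents give no f; 30% and 50% are assumptions. The control rate becomes 0.76/(1 − f), that is 1.09 or 1.52, so b = 0.33 or 0.76 attendances per child are added.

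If the drug does not affect the added visits, the rate ratio is (1 − f) × 0.67 + f = 0.77 or 0.84. Two variance assumptions are shown. Shared overdispersion keeps k = 1.26 for the whole count. Independent Poisson makes the variance of an arm with wheeze mean m equal to m + k·m² + b.

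| Main-effect power, 1222 evaluable | f = 30% | f = 50% |
|---|---|---|
| No effect on added visits, shared overdispersion | 85% | 61% |
| No effect on added visits, independent Poisson | 95% | 89% |
| 33% reduction on all visits (k = 1.26) | over 99% | over 99% |

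**4. Genotype interaction at N = 1200** (10.2.1: reductions of 60% and 20%, just over 80% power). The variances are summed over the two strata. The variant share is not given. Solving 60%·s + 20%·(1 − s) = 33% gives s = 0.325; s = 0.25 is a second assumption.

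| Interaction power, no effect on added visits | s = 0.25 | s = 0.325 |
|---|---|---|
| Wheeze only | 81% | 87% |
| f = 30%, shared / independent | 47% / 63% | 54% / 70% |
| f = 50%, shared / independent | 26% / 47% | 30% / 53% |

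**5. Unit alone.** Suppose 20% to 50% of episodes produce two attendances and the effect is the same. The control count rises from 0.76 to between 0.91 and 1.14. Power at N = 1050 goes from 89.6% to about 88% (two means), or from about 96% to about 95% (negative binomial).

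**The case against.** The best reply is that 10.1.1 is the only text headed as the primary endpoint and is explicit on cause, unit, period and source. The Summary objective agrees with its broad cause. Section 10.1.2 lists wheeze-specific GP, A&E and admission outcomes as secondary, which fits a deliberately broader primary. Definition 1 in 10.1.3 is not labelled primary, and definition 2 uses it as a severity criterion for time to first severe wheeze.

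This has weight, and it rules out saying that a wheeze-only endpoint was plainly intended. It does not remove the conflict. The Summary states both the primary objective and the primary analysis in essentially the term that definition 1 defines, Section 2 gives the principal objective as wheeze alone, and 10.2.1 powers a wheeze count. If 10.1.1 governs, the powered quantity is not an endpoint anywhere, because 10.1.2 lists the wheeze contacts separately and never as a combined episode count.

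A reader might also infer that the sample size is miscalculated, or that the trial is underpowered for its primary endpoint. The documents support neither. The 1050 roughly follows from its inputs. A loss of power needs an assumed non-wheeze share and an assumed absence of drug effect on those visits, yet reducing visits for infection is part of the Summary objective. If all visits fell by 33%, power would rise. The size of any loss also depends heavily on whether the added counts share the child's overdispersion.

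**Conclusion.** The point holds as an inconsistency in the primary endpoint, mainly on cause. The stated power is supported for a wheeze-attack count measured by an oral-steroid proxy. It is not supported for the endpoint in 10.1.1, for which the protocol gives no rate, SD or effect.

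The direction and size of the change cannot be fixed from the documents. On the assumptions shown, main-effect power could lie anywhere from 61% to over 99%, against 98% for the wheeze-only count by the same method. Interaction power could fall from 81–87% to 26–54% with shared overdispersion, or to 47–70% with independent Poisson additions, if the drug does not affect non-wheeze visits. The unit conflict changes the reported counts but hardly changes power when the effect is the same.

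**What to change.** Before unblinding:

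- Choose one qualifying cause and one unit of count, with a written rule for linked GP and A&E contacts.
- Make the Study Summary, Section 2, 10.1.1, 10.1.3 and 10.2.1 identical on this.
- Restate the control rate, SD, effect and power (main effect and interaction) for the chosen endpoint.
- Keep the other count as a named secondary endpoint. If the all-respiratory count stays primary, list the combined count of clinician-diagnosed wheeze episodes with unscheduled attendance. If the wheeze count becomes primary, list the all-respiratory count.

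Which cause to choose is for the sponsor, as the documents do not settle it. Clinical records are already used to confirm attendances. The cost is a protocol amendment, new justification of the sample-size inputs, and possibly a less favourable stated power.
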